#### **5. Study Intervention/Investigational Agent**

This is a non-randomized, controlled, non-blinded, single-arm pilot study trial, with an adaptive design at mid-trial. After 10 participants complete the study, an interim analysis will be performed and recruitment will either continue with no change to the protocol or, changes may occur in regard to the STAR particle application area, position, pressure, or rubbing cycle in an adaptive design manner.

The trial will be performed in a climatized room and participants will have time to adapt and cool down to decrease risk of modulation TEWL reading.

The investigational agent will be STAR particles made of titanium dioxide, a widely used and safe ceramic material found in sunscreens, cosmetics, and paint. The star-shaped geometry is designed to inhibit complete insertion of the particle into skin, so STAR particles do not remain embedded in the skin. After the arms of the STAR particle puncture the skin, the elastic forces of the skin push the particles out. The STAR particles will be mixed with a gel formulation of the following composition: 0.7%w/w Xanthan Gum + 2.5%w/w Hydroxypropyl methylcellulose + Cyclomethicone and Dimethicone. STAR particles will be produced by Aldena Therapeutics under GMP conditions.

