#### **Application of STAR particles to volar side of each forearm (Figure 1)**

1. Wash participant's arms and hands with disinfecting soap before any application.
2. Allowed skin to dry for at least 10 minutes.
3. Investigator to delimit the 9 areas on participant's forearms and hand with a marker.
4. Measure TEWL  $T_0$  on all 9 sites - measure from areas 1 to 9 and then from 9 to 1, giving 2 measurements for each time point according to Figure 1.
5. Apply STARS (80KPa for 60 cycles) on the dorsum of the closed hand.

6. Apply STARs (80KPa for 60 cycles) to the palmar surface of the same hand.
7. Apply STARs (pressure and # of cycles) to the six areas on the forearms per Figure 1.
8. Extra care will be taken to wash arms and hand with warm water to remove the STAR particles and gel and allowed to dry at least 5 min before the next TEWL ( $T_{20}$ ) is taken.
9. Measure TEWL  $T_{20}$  on all 9 sites - measure from areas 1 to 9 and then from 9 to 1, giving 2 measurements for each time point according to Figure 1.
10. Participant completes Tolerability Questionnaire
11. Participant completes Removal & Disposal Questionnaire and User's Feedback Questionnaire.
12. Pictures (3) will be taken to assess erythema: both forearms and the hand
13. Measure TEWL  $T_{30}$  on all 9 sites - measure from areas 1 to 9 and then from 9 to 1, giving 2 measurements for each time point according to Figure 1.
14. Apply GV staining for 10 minutes on the 2 arms resting with volar arm upward and right hand on a gauze containing GV stain.
15. Wash and wipe off the GV stain thoroughly with ethanol 70%.
16. Take 3 photos of each site to visualize the puncture after GV staining.
17. Using 2 fingers (index and middle), the participant will apply pressure to a kitchen scale in an effort to mimic application of low, medium, and high pressures.
18. The investigator records the weight (from the scale) when the pressure is constant.
19. Participant is discharged.

**Figure 1:** STAR particle application sites for V1 (participants #1-10)

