**Application of STAR particles to volar side of each forearm**

20. Wash participant's arms and face with disinfecting soap before any application.
21. Allowed skin to dry for at least 10 minutes.
22. Investigator to delimit the 9 areas on participant's forearms and face with a marker.
23. Measure TEWL  $T_0$  on all 4 sites - measure from areas 1 to 4 and then from 4 to 1, giving 2 measurements for each time point.
24. Apply STARs (80KPa for 60 cycles) on the forearm.
25. Apply STARs (80KPa for 60 cycles) to the side of the face.
26. Apply gel without STARs on the other forearm and on the other side of the face.
27. The study team will take photos of the application sites.
28. After approximately 5 minutes, the gel (with or without STAR particles) will be removed with a dry tissue or gauze.
29. The study team will take photos of the areas of application.
30. After the gel is removed in all areas, the investigator will examine the participant to check if there are any remaining STAR particles on the participant and/or the surrounding environment.
31. Participant completes Tolerability Questionnaire
32. Participant completes Removal & Disposal Questionnaire and User's Feedback Questionnaire.
33. Pictures (3) will be taken to assess erythema: both forearms and the face
34. Measure TEWL  $T_{30}$  on all 4 sites - measure from areas 1 to 4 and then from 4 to 1, giving 2 measurements for each time point.
35. Apply GV staining for 10 minutes on the 2 arms resting with volar arm upward and right hand on a gauze containing GV stain.
36. Wash and wipe off the GV stain thoroughly with ethanol 70%.
37. Take 3 photos of each site to visualize the puncture after GV staining.
38. Using 2 fingers (index and middle), the participant will apply pressure to a kitchen scale in an effort to mimic application of low, medium, and high pressures.
39. The investigator records the weight (from the scale) when the pressure is constant.
40. Participant is discharged.

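### In participants 11-20 the gel is wiped off dry, with no wash before T30 TEWL or GV staining, so residual gel may alter these readings

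*Protocol*

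**What the plan says.** Protocol section 4 builds the primary endpoint on two measures: GV-stained perforations per unit area, and TEWL before and after application.

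For participants 11-20 (section 6.D) the baseline preparation is "Wash participant's arms and face with disinfecting soap before any application" (step 20), then "Allowed skin to dry for at least 10 minutes" (step 21), then T0 TEWL (step 23). STAR gel goes on one forearm and one side of the face at 80 kPa for 60 cycles (steps 24-25), and STAR-free gel on the opposite sides (step 26). Removal is described in step 28: "After approximately 5 minutes, the gel (with or without STAR particles) will be removed with a dry tissue or gauze". Step 30 has the investigator "check if there are any remaining STAR particles on the participant and/or the surrounding environment"; it does not ask about remaining gel. After questionnaires and erythema photographs (steps 31-33), T30 TEWL is taken "on all 4 sites - measure from areas 1 to 4 and then from 4 to 1" (step 34), and GV is applied (step 35). The first liquid cleaning after application is the 70% ethanol of step 36, once the stain is already on.

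For participants 1-10 (section 6.C, step 8) the instruction differs: "Extra care will be taken to wash arms and hand with warm water to remove the STAR particles and gel", with at least 5 minutes of drying before the next TEWL.

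Section 5 gives the gel as "0.7%w/w Xanthan Gum + 2.5%w/w Hydroxypropyl methylcellulose + Cyclomethicone and Dimethicone".

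**The concern.** A before-after TEWL change is interpretable as perforation only if nothing else about the skin surface differs between the two readings. In participants 11-20 the surface is washed and dried at T0, but wiped without liquid at T30. If the wipe leaves gel behind, the TEWL change mixes perforation with residue, and the GV stain meets a surface that may still carry gel. The protocol itself treats washing off the gel as the step that precedes post-application measurement in participants 1-10. It gives no reason for dropping the wash in the second cohort.

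At stake are the second cohort's before-after TEWL on forearm and face, its forearm GV result, and any reading of 80 kPa/60 cycles across the two cohorts. That setting is measured on washed skin in one cohort and on dry-wiped skin in the other.

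**Working it through.** The protocol has no figure to reproduce here. The check sets the two procedure lists side by side.

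| Stage | Participants 1-10 (6.C) | Participants 11-20 (6.D) |
|---|---|---|
| Before T0 | Soap wash, at least 10 min drying (steps 1-2) | Soap wash, at least 10 min drying (steps 20-21) |
| Removal of gel | Warm-water wash, at least 5 min drying (step 8) | Dry wipe after about 5 min (step 28) |
| Post-application TEWL | T20 and T30 (steps 9, 13) | T30 only (step 34) |
| GV | After T30 (step 14) | After T30 (step 35); arms and right hand, not face |
| Any wash between removal and TEWL/GV | The removal is itself a wash | None |

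**Readings exposed.** 4 sites x 2 passes x 10 participants = 80 post-application TEWL readings. Two of the four sites are on the face, so 2 x 2 x 10 = 40 of these are face readings. No other cohort supplies face TEWL. The schedule in section 9 lists T20 without separating the cohorts, but the 6.D steps contain no T20. A T20 taken after step 28 would have the same problem.

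**Illustration on assumed values.** Neither the residual effect nor the true TEWL rise is given. Assume that STAR particles raise TEWL by 50% of T0, that gel alone has no true effect, and that residue lowers every post-application reading by a fraction f (a negative f means that it raises the reading).

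- STAR before-after change = 1.5(1 - f) - 1
- Control before-after change = (1 - f) - 1 = -f
- STAR minus control = 0.5(1 - f)
- STAR/control ratio of post-to-T0 values = 1.5(1 - f)/(1 - f) = 1.5

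| f | STAR change | Control change | STAR minus control |
|---|---|---|---|
| -0.30 | +95% | +30% | 65 points |
| -0.10 | +65% | +10% | 55 points |
| 0 | +50% | 0% | 50 points |
| 0.10 | +35% | -10% | 45 points |
| 0.20 | +20% | -20% | 40 points |
| 0.30 | +5% | -30% | 35 points |

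The before-after change is distorted strongly and the difference from control moderately. The ratio is not distorted at all, provided that f is the same on both sides. If residue differs, with f = 0.20 on the STAR side and 0.10 on the control side, the ratio becomes 1.5 x 0.80/0.90 = 1.33. With the values swapped it is 1.5 x 0.90/0.80 = 1.69.

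**The case against.** The strongest reply is that nothing in the protocol says gel remains. Step 28 calls the dry wipe a removal, and step 30 proceeds as though it were complete. Section 5 lists the ingredients without describing how they behave on skin. Step 8 shows that washing was chosen for participants 1-10; it does not show that wiping leaves enough to matter. This stands: residue is an inference, and only the missing wash is a fact.

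The same-participant gel-only control is also a real safeguard. It is wiped in the same way, and under a proportional effect equal on both sides the STAR/control ratio is untouched. This stands in part. Section 4 is worded as before and after application, and equal residue on the two sides is itself unverified.

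Dry removal also fits the exploratory aim of assessing dispersion and disposal (section 2.C), and it is written into the current protocol, so it is not an unannounced mid-trial change. That is a reason to keep the wipe. It is not a reason to measure TEWL and GV straight after it.

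A reader might go further and infer that the primary measures are in fact read through a gel film, that every GV photograph and every face result is affected, or that the choice of pressure and cycles is compromised. The documents do not support these readings:

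- No film is documented.
- Step 35 does not stain the face, so face GV is not at issue.
- Face photographs, the particle check and the questionnaires are neither TEWL nor GV readings.
- Participants 11-20 receive a single setting, so the ranking of pressures and cycles comes from participants 1-10.
- No plan to pool the cohorts is stated.

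**Conclusion.** The point holds as a measurement risk that is avoidable and unexplained. In participants 11-20, skin preparation differs between T0 and T30, and between this cohort and participants 1-10. It may affect all 80 post-application TEWL readings of the cohort, including all face TEWL, and the forearm GV staining. Size and direction are unknown; the illustration rests on assumed values and shows only which comparisons are vulnerable. The before-after TEWL change and any cross-cohort comparison at 80 kPa/60 cycles are unprotected. The STAR-versus-gel contrast within the cohort is partly protected, and fully so only if residue acts proportionally and equally on both sides. The conclusion assumes that the 6.D steps are carried out as written, with no unrecorded wash. For a 20-person feasibility pilot this should be corrected, but it does not invalidate the study.

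**What to change.** Leave steps 28-33 as they are, so that the dry-removal assessment, particle check, questionnaires and erythema photographs are undisturbed. Before step 34, add a wash of all four sites as in step 8, then a fixed drying time, and only then take T30 TEWL and apply GV. Restate the T30 label as the actual time after application.

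Step 8 uses warm water and at least 5 minutes of drying, while T0 follows soap and at least 10 minutes. The match to baseline will therefore be close but not exact, as it already is for participants 1-10. Fixing the drying time at the T0 duration would narrow the gap.

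The cost is about 15 minutes per participant (this review's estimate), or 10 x 15 = 150 minutes over the cohort, with no new equipment. TEWL and GV are also read somewhat later after application.

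If the sponsor prefers dry removal only, the protocol should say so. It should base TEWL and GV conclusions for participants 11-20 on STAR versus gel control within that cohort, and state that they will not be pooled or compared with participants 1-10.

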**7. Data Specimen Banking**

This study will not be banking any specimens or data.

**8. Sharing of Results with Participants**

There are no expected incidental findings for the study. Results will not be returned to the participant.

**9. Study Timelines**

- Each subject will participate in the study for the 1 visit.

- The duration anticipated enrolling all study participants is 3 months.
- The estimated date for the investigators to complete this study (complete primary analyses) is 12 months.

### **Study Procedures and Assessments**

Procedures and Assessments	Visit	1-30 days post Visit
Informed consent	X	
Medical history	X	
Inclusion and exclusion criteria	X	
Anthropometric Information	X	
Physical examination of Skin	X	
Label treating zones (9)	X	
TEWL ( $T_0$ )	X	
STAR particle application	X	
TEWL ( $T_{20}$ )	X	
Complete Questionnaires	X	
VAPS & Disposal	X	
Photograph (Erythema)	X	
TEWL ( $T_{30}$ )	X	
GV Staining	X	
Picture of GV Staining	X	
Test Pressure (on Scale)	X	
AE Reporting	X	X

### **10. Inclusion and Exclusion Criteria**

- 1) Inclusion criteria:
  - a. Adult, 18 – 39 years of age
  - b. In good general health as determined by a medical history
  - c. Willing and able to provide informed consent and follow all study requirements
  - d. Not pregnant and does not desire to become pregnant in subsequent two months.
    - a. Verbally confirmed with participant during consent process.

2) Exclusion criteria:

- a. Has a known allergy or sensitivity to .7%w/w Xanthan Gum + 2.5%w/w Hydroxypropyl methylcellulose + Cyclomethicone and Dimethicone or alumina
- b. Has any skin disorders or skin allergies
- c. Has any medical condition that may affect skin or skin sensation
- d. Has abnormal (e.g., tattooed) skin at forearms or face
- e. Has known neurological condition affecting sensory function or perception of pain
- f. Has inflammatory bowel disease
- g. Has applied skin ointment or cream to forearms in the previous 24 hours
- h. Has a major congenital or chromosomal abnormality known to affect skin
- i. Has taken pain medication in the last 24 hours
- j. Is currently participating in another interventional clinical trial
- k. Has previously participated in a STAR particle interventional clinical trial
- l. Has any condition (social or medical), which in the opinion of the investigator would make study participation unsafe, would interfere with adherence to the clinical study requirements, or would complicate data interpretation

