**15. Risk to Participants**

---

The risks to this study are minimal. We will be applying STAR particles that should puncture the skin, and due to the elastic forces of the skin, will push the particles out. From the time the STAR particles are applied to the skin, the possible risks would be expected to be local skin reactions at the site of STAR particle application including erythema, edema, tenderness, bleeding, and/or bruising.

A systemic reaction would be unlikely to occur, but due to the potential that the application and retention of STAR particles in the skin could facilitate bacterial entry into the skin, in addition to the local reactions listed above, systemic reactions including fever, cough, nausea, vomiting, diarrhea, fatigue, and headaches could also occur. Based on previous human research with STAR particles, local and systemic reactions are unlikely to occur (1). Acute skin reactions (ASRs) will be scored quantitatively with qualitative remarks as needed. The application of the STAR particles is expected to have a minimal risk to the subject. It is possible subjects could describe the placement of the STAR particles as uncomfortable or painful but based on previous human studies (1) this seems less likely. We will take precautions to prevent infections, such as using sterilized or low bioburden materials and wiping the skin with an alcohol swab before the study.

We hypothesize that the STAR particles will not remain in the skin. Our previous research on STAR particles suggests that the risk for application of STAR particles to be minimal (1).

These particles are made of titanium dioxide, a widely used and safe ceramic material found in sunscreens, cosmetics, and paint. STAR particles are designed to incorporate invisibly into topical formulations applied to skin similarly to conventional topical skin products. Based on previous clinical studies and FDA approvals of other drugs/devices using these materials, we therefore expect non-significant risk.

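### The allergy exclusion names alumina, while the protocol describes the particles as titanium dioxide; the criterion and the product description disagree and need reconciling.

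*Protocol*

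**What the plan says.** Section 5 (Study Intervention/Investigational Agent) gives the particle material: "The investigational agent will be STAR particles made of titanium dioxide". It gives the gel as "0.7%w/w Xanthan Gum + 2.5%w/w Hydroxypropyl methylcellulose + Cyclomethicone and Dimethicone". Section 15 (Risk to Participants) repeats the particle material: "These particles are made of titanium dioxide". The Study Summary in Section 1 is less specific and speaks only of biocompatible materials.

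Exclusion a in Section 10 covers known allergy or sensitivity. It lists the same gel ingredients as Section 5 and closes with "Cyclomethicone and Dimethicone or alumina".

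Two other exclusions in Section 10 bear on the point. Exclusion b removes anyone who "Has any skin disorders or skin allergies". Exclusion l removes anyone with a social or medical condition "which in the opinion of the investigator would make study participation unsafe", or that would interfere with adherence or complicate interpretation of the data.

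**The concern.** Exclusion a is the one criterion that lists product components by name. One would expect it to cover what is put on the skin: the gel and the particles. The gel is covered. In the place where the particle material would be expected there is alumina, which the protocol mentions nowhere else, and the stated particle material is absent.

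The mismatch matters whichever statement is wrong.

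- If Sections 5 and 15 are right, the allergy criterion omits the material intended to puncture the stratum corneum and names one that is not in the described product.
- If exclusion a reflects the true composition, Sections 5 and 15 misdescribe the investigational agent. Section 15 also bases its expectation of non-significant risk on earlier clinical studies and regulatory approvals involving the stated materials, so that reasoning would have to be looked at again.

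Section 13 says that eligibility is established by asking participants questions and examining their skin. A known sensitivity in someone whose skin looks normal on the day can come to light only through the questions, and exclusion a is the criterion that tells the investigator which materials to ask about.

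**Working it through.** No arithmetic applies. No figure in the protocol rests on this criterion, so there is nothing to reproduce. The check is to set each statement of composition beside the criterion.

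| Component | Section 1 | Section 5 | Section 15 | Section 10, exclusion a |
|---|---|---|---|---|
| Particles | biocompatible materials, not specified | titanium dioxide | titanium dioxide | titanium dioxide not named |
| Gel | not given | xanthan gum, hydroxypropyl methylcellulose, cyclomethicone, dimethicone | not given | the same four ingredients |
| Alumina | not mentioned | not mentioned | not mentioned | named |

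1. **Gel.** The four ingredients in exclusion a match the four in Section 5. The Revision History records that this gel came in with revision 4.1, so the gel part of the criterion is in step with the current product. The mismatch is confined to the particle material.
2. **Particles.** The two sections that name a particle material agree with each other. Exclusion a does not name that material.
3. **Alumina.** It occurs once in the protocol, in exclusion a. It is not listed as a particle material or as a gel ingredient.
4. **Other criteria.** Titanium dioxide appears in none of the inclusion or exclusion criteria.
5. **Who could pass.** Take a person with a known sensitivity to titanium dioxide.
   - Exclusion a does not apply to them as worded.
   - Exclusion b applies if the sensitivity is a skin allergy and the person reports it as one. A known contact allergy would probably be caught here.
   - Exclusion l applies if the investigator learns of the sensitivity and judges it relevant.
   - What remains is mainly a known sensitivity that the person does not think of as a skin allergy and that no question brings out. Exclusion a speaks of allergy or sensitivity, which is wider than the skin allergies in exclusion b, so the two do not fully overlap.
6. **Which statement is wrong.** Sections 5 and 15 agree and exclusion a stands alone. That makes an error in exclusion a the simpler reading, but it does not prove it. Nothing else in the protocol settles the composition.

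**The case against.** The strongest reply is that failing to meet exclusion a is not the same as passing screening. Exclusion b is broad, and a known allergic skin reaction to a sunscreen or cosmetic fits its wording; exclusion l adds discretion. This stands, and it is why the gap is narrow. It does not remove the point. Neither criterion prompts a question about the particle material, and the mismatch in the text remains whatever the other criteria catch.

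A second reply is that the screening form is not among the documents, so the questions put to participants are unknown. This also stands. What can be shown is that the written criterion does not name the stated material, not that staff ask about the wrong one.

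Three stronger readings are tempting, and the protocol does not support them.

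- A reader might infer that a reaction in a sensitive participant would contaminate the tolerability and adverse event results. Recording reactions to the particles is what those secondary endpoints in Section 4 are for, so counting one is not a bias. Participants also receive gel without particles at a control site. No effect on the primary endpoint (perforations per square centimetre and transepidermal water loss) follows either.
- A reader might say that the error affects all 20 participants. All 20 are screened under the criterion, but that is not the number misclassified or put at risk, which the protocol gives no means of estimating.
- A reader might take it as settled that alumina is the mistake. The protocol alone does not establish that.

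**Conclusion.** The point holds as an internal inconsistency in a safety-related eligibility criterion. Exclusion a names a material found in no described component of the product and omits the material that Sections 5 and 15 say the particles are made of.

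The practical size is small. Exclusions b and l would probably catch most known cases, and the remainder is mainly a sensitivity not reported as a skin allergy. The number of such people cannot be derived from the protocol. There is no consequence for sample size, power or error rate.

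The conclusion rests on reading the current text of Sections 1, 5, 10 and 15 as it stands. It does not assume which statement is correct, nor what the screening form or consent materials contain. It is worth correcting because the criterion concerns participant safety, the contradiction is plain on the page, and the correction is simple.

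**What to change.** Confirm the particle composition with the manufacturer, then make Sections 5, 10 and 15 agree.

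- If Sections 5 and 15 are right, exclusion a should name titanium dioxide alongside the gel ingredients and should no longer name alumina.
- If Sections 5 and 15 are the ones in error, correct the composition in both, and revisit the risk statement in Section 15 that relies on it.
- If the particles contain both materials, the composition statements and exclusion a should each say so.

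In every case exclusion a should name what participants are exposed to and nothing that is absent from the product. In the first case the cost is about one word in the criterion, with the screening form checked to match. In the other two it also includes rewording Sections 5 and 15. None of the three calls for a change to the design, the sample size or the analysis.

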### **C. Participants 1-10**

Enrolled healthy adults will receive eight applications (three on each forearm and two to one hand) of STAR particles and one control application on the volar side of one of the forearms for a total of nine applications to the forearms. In addition, two applications of STAR particles will be applied to one of the hands – one application to the palmar surface and one to the dorsum of the hand (Figure 1).

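### The 24-hour cream exclusion covers the forearms only and the abnormal-skin exclusion omits the hand, although STAR particles are applied and TEWL is read on the hand and face as well

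*Protocol*

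**What the plan says.** Two exclusions in Protocol section 10 are tied to body sites. Exclusion g applies to a person who "Has applied skin ointment or cream to forearms in the previous 24 hours". Exclusion d applies to a person who "Has abnormal (e.g., tattooed) skin at forearms or face".

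The treated sites are wider than either list. Under section 6.C, participants 1-10 "receive eight applications (three on each forearm and two to one hand) of STAR particles and one control application on the volar side" of one forearm. The hand sites are "one application to the palmar surface and one to the dorsum of the hand". TEWL is then taken "on all 9 sites - measure from areas 1 to 9 and then from 9 to 1", and the GV stain is applied to both arms and the right hand (step 14). For participants 11-20, section 6.D step 25 reads "Apply STARs (80KPa for 60 cycles) to the side of the face". Step 26 puts gel without particles on the other forearm and the other side of the face, and TEWL is measured at all four sites.

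Section 4.A builds the primary endpoint on GV perforation counts and on TEWL before and after application. The Revision History records that version 4.1 added the face as an application site.

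**The concern.** The protocol treats cream within 24 hours and abnormal skin as reasons to exclude someone when they concern the forearm. The same TEWL method is used on the hand and face, and the same GV stain on the hand. No reason is given for a looser rule at those sites. Exclusion d names the face and exclusion g, in the same list, does not, which looks like an incomplete alignment with the current sites.

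As written, someone who put cream on the face or hand that morning is not excluded by g, and someone with a tattooed hand is not excluded by d. Residue could shift the T0 TEWL value or change how the particles rub against the skin. A tattoo could make stained perforations harder to see. What is at stake is the quality of the hand and face readings in a pilot of 20 people.

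**Working it through.** The plan states no figure on this point, so there is none to reproduce. The check compares the treated and measured sites with the sites each exclusion names, and then counts.

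**Inputs**
- Participants 1-10 (section 6.C): 6 forearm STAR sites + 1 forearm control + 2 hand sites = 9 sites.
- Participants 11-20 (section 6.D, steps 23-26): 1 forearm STAR + 1 forearm gel + 1 face STAR + 1 face gel = 4 sites. The count follows the TEWL and application steps. Other counts given in section 6.D (eight applications, nine areas to mark) do not fit the four sites described and are a separate matter.
- 10 participants per cohort.

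**Coverage by site**

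| Site | Cohort | Exclusion g (cream) | Exclusion d (abnormal skin) | Reading exposed |
|---|---|---|---|---|
| Forearm | both | named | named | none |
| Hand, palm and dorsum | 1-10 | not named | not named | TEWL, GV |
| Face, both sides | 11-20 | not named | named | TEWL |

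For the face, step 35 lists the two arms and the right hand for GV staining and does not list the face. As the text stands, the only primary-endpoint reading there is TEWL.

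**Counts**
- Planned participant-sites: 10 × 9 + 10 × 4 = 130.
- Outside exclusion g: 10 × 2 (hand) + 10 × 2 (face) = 40, and 40/130 = 31%. By cohort this is 2 of 9 and 2 of 4 sites per person.
- Outside exclusion d: 10 × 2 (hand) = 20, and 20/130 = 15%, all in participants 1-10.

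These are counts of sites without a stated rule. They do not measure bias.

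**Which comparisons are touched**
- Section 6.B sets three pressures and two cycle counts: 3 × 2 = 6 combinations. Six forearm sites receive STAR particles. Figure 1 is not available here, so one combination per site is an inference. In any case both exclusions name the forearm.
- The two hand sites and the face all receive one fixed condition, 80 kPa for 60 cycles. They add nothing to a ranking of pressures or cycle counts. They describe how that one condition performs on other skin.

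**Whether other provisions close the gap**
- Soap wash before T0: covers arms and hands in participants 1-10, and arms and face in participants 11-20. The forearms get the same wash and still carry the 24-hour rule, so the protocol does not treat washing as enough.
- Same-site T0: removes a shift that stays constant from before to after. It does not remove an effect of residue on the rubbing itself.
- General exclusions: "Has any skin disorders or skin allergies" has no site limit, but neither cream use nor a tattoo is plainly a disorder. Exclusion l covers a condition that in the investigator's opinion "would interfere with adherence to the clinical study requirements, or would complicate data interpretation". That is discretionary and does not prompt anyone to ask about cream.

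**The case against.** The strongest case on the other side is that the practical effect is small. Every site is washed and dried for at least 10 minutes before T0. Each site has its own baseline. The face has a gel control on the opposite side. Skin is examined at the visit, and the investigator can exclude on judgement. The hand part may also be moot: version 4.1 added the face, and section 5 allows the application area to change after 10 participants, so participants 1-10 may already have been complete. The document does not say. All of this stands as a reason to rate the point low. It does not explain why the cream rule names one treated region and leaves out two others.

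Three stronger readings are tempting and are not supported:
- *Nothing cancels on the hand because it has no control site.* There is indeed no hand control, but T0 is taken at each hand site, so a stable shift drops out of the before-after change.
- *GV counts on the face are distorted.* Step 35 does not name the face for staining. It names the right hand, which this cohort does not have treated; that is a separate inconsistency.
- *The choice of pressure and minimum cycles is compromised.* That comparison rests on forearm sites, which both exclusions cover.

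How common cream use is on the face and hands, and how far it moves TEWL, cannot be taken from the documents. The point does not depend on either.

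**Conclusion.** The gap in the wording is real and the point is minor. Exclusion g omits the hand and the face, and exclusion d omits the hand, although primary-endpoint readings are taken there. The cream rule is missing at 40 of 130 planned participant-sites, and the abnormal-skin rule at 20 of 130. The possible consequences are a disturbed T0 TEWL or altered rubbing at the hand and face, and harder GV reading on a tattooed hand. Wash, baseline and facial control reduce the first of these without guaranteeing its removal. The size cannot be derived from the documents, so this is a risk and not a demonstrated bias.

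The conclusion assumes 9 and 4 sites per person as set out in the procedure steps, and that the reason for the forearm rule applies equally at the other sites, since the protocol gives none for a difference.

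**What to change.** Word exclusions d and g so that both apply *at any application site*. In practice that means forearms and face for participants 11-20, and forearms and hand for participants 1-10 if any remain to be enrolled. Add the question about recent cream to the recruitment contact, so that volunteers know before they attend.

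If participants 1-10 are complete, no eligibility change can help them. In that case, state when the hand readings are interpreted that recent cream use and abnormal skin on the hand were not specifically excluded.

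The cost is a few words in section 10 and a recruitment reminder. Some volunteers will have to skip moisturiser for a day or be rescheduled.
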